To determine if the intraocular pseudophakic contact lens (IOPCL), referred to as the AccuraSee, provides refractive correction using a plus powered lens in subjects with ocular pathology previously implanted with a Bausch and Lomb LI61AO or LI61SE monofocal posterior chamber intraocular lens (PCIOL) and to confirm its positional stability and adherence relative to the PCIOL.

Study Design:

This will be a 12-month three center study, in which a maximum of 10 pseudophakic subjects will be enrolled.

This study is being conducted in accordance with 21 CFR Parts 50, 54, 56 and 812.42 (U.S.C 282(j)). ISO 14155 Clinical investigation of Medical Devices for Human Subjects, ISO 11979-7, and the ethical principles laid down in the Declaration of Helsinki.

1. Introduction and Rationale

The AccuraSee (intraocular pseudophakic contact lens) consists of a 4.5 mm diameter concave-convex optic with three opposing haptic straps, or tabs. The haptic straps are designed to enter and rest within three channels created under the anterior leaflet of the capsular bag. Each channel is created with a Cady-Soiseth Capsule Separator spatula. Each haptic strap or tab has a small pawl, or ridge on the bottom that is used to catch and lock on to the IOL optic edge. This pawl aids in both centering the AccuraSee on the IOL optic as well as allowing the haptic strap to stay securely seated while contained under the surface tension of the anterior leaflet of the capsular bag. The lens is designed to fine-tune the residual refractive error of the longstanding pseudophakic eye. The lens design, position and surgical approach are intended to lessen the complication rate and overall invasive nature of today's available secondary lens implantation technologies.

2. Study Objective

The primary objective of this study is to determine the stability of the AccuraSee to successfully adhere to a pseudophakic intraocular lens without rotation or slippage.

The secondary objective of this study is to determine if the AccuraSee can successfully change refraction up to +3.0 diopters (D) in subjects previously implanted with an Bausch and Lomb LI61AO and LI61SE monofocal intraocular lens.

Safety Endpoints

- Preservation of BCDVA Proportion of eyes (< 5%) that lose two or more lines of BCDVA from baseline.
- Successful delivery of the IOPCL as determined at 7-14 days post-operative
 - o No capsular tear
 - o Visualize centration between the PCIOL and IOPCL

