 - o No visible damage to either the PCIOL or the IOPCL
 - o Uniform leaflet coverage of all IOPCL haptic tabs
- Long-term adherence and positional stability
 - Minimal Change in uniformity of the gap between 1-2 months and 4-6-months as determined by UBM measurements. Minimal change is defined as +/- 10 microns between visits is established and maintained using UBM imaging
- Characterization and incidence of cumulative and persistent intraoperative and post-operative adverse events.

Stopping Rules

The Sponsor or the clinical investigator can suggest suspension of the clinical trial at any time if they are in receipt of information that leads them to believe that continuing the study jeopardizes the health and welfare of the clinical trial participants. Suspension of the study will be considered if two or more consecutive severe ocular injuries occur at any one clinical site that are related to the surgical procedure and/or IOPCL device. A severe ocular injury results in a permanent impairment of a vision or permanent damage to an eye.

Examples:

- Uveitis-Glaucoma-Hyphema (UGH) Syndrome. Intraocular chafing from the IOL/PCIOL implant leading to a spectrum of iris transillumination defects and pigmentary dispersion to microhyphemas with elevated intraocular pressure.
- Posterior capsule rupture with IOL/PCIOL dislocation resulting in a posterior vitrectomy during the surgical procedure

Primary Effectiveness Endpoint

Proportion of eyes ($\geq 50\%$) able to achieve a stable target refraction, (manifest or autorefraction) within 0.5 D of the intended target. Stability is achieved when there is no change (± 0.50 D) within two consecutive postoperative visits at 1 month or later visits.

04-08-2021 5

3. Subject Population

A maximum of 10 pseudophakic eyes will be implanted unilaterally with the AccuraSee IOPCL.

3.1. Inclusion Criteria:

- 1. Subjects who have already had cataract surgery with a Bausch and Lomb monofocal intraocular lens model LI61A0 (with lens power from 18.0 diopters (D) to 23.0 D) or model LI61SE (with a lens power from18.0 D to 22.5 D), as clearly evidenced by photographic documentation with one of the following: (1) patient medical record, (2) clinic chart with labeling attached, (3) surgical record with labeling attached, or (4) patient identification card with make, model, power, and serial number.
- 2. Able to comprehend and sign a statement of informed consent.

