cannula on a 5cc syringe filled with BSS to vigorously irrigate the space between the two lenses. If for some reason the vigorous irrigation did not remove all the debris from the inter-lenticular space carefully release the haptic/tabs of the IOPCL closest to the location of the debris and continue to irrigate. If this approach is unsuccessful consider removing the IOPCL, irrigate the surface debris on the surface of the IOL and replace it with another IOPCL. If the debris attached to the surface of the IOL remains adhered after the final attempt to irrigate do not introduce a new IOPCL. At the conclusion of the case, please record in detail on the CRF every and all steps taken to remove the cellular material between the two lenses.

REMOVAL OF THE IOPCL

Re-open the initial incisions or create new access into the anterior chamber if they have healed. With ProVisc in the anterior chamber use a Sinskey hook or similar instrument to disengage the three IOPCL haptics from their respective channels. Place a small amount of ProVisc between the IOPCL and existing PCIOL to separate them apart. Using microforceps thru the 2.0 mm wide incision, grasp the anterior and posterior surface of the IOPCL and remove it through the incision. The IOPCL is flexible and will fold and achieve a "taco" form for removal in one piece. After explantation of the complete IOPCL, assess the lens surface of the existing PCIOL for any damage. If any damage is noticed on the existing PCIOL particularly on its lens surface, please record this on the IOPCL removal Case Report Form. Remove the remaining ProVisc, irrigate and close the wound per your normal IOL procedures.

Please return the removed IOPCL to the Sponsor for damage assessment.

YAG CAPSULOTOMY

A Nd:YAG capsulotomy is not allowed to treat opacity between the IOPCL and PCIOL after implanting the IOPCL. Irrigation should be performed to remove the cellular matter from the lens(es) See page 10 for irrigation instructions

If clinically significant PCO is observed on the posterior side of the PCIOL, treatment using standard Nd:YAG capsulotomy is allowed. Nd: YAG capsulotomy should not be performed prior to 12 weeks post IOPCL implantation.

10. Examination Schedule

Subjects will be examined and evaluated according to the following schedule of visits.

Form OA – Pre-Operative Operative (Form OB)

Form 1 (1 to 2 days postoperative)

Form 2 (7-14 days postoperative)

Form 3 (30-60 days postoperative)

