10.2 Unscheduled / Interim Visits

Additional visits may be scheduled as deemed necessary by the investigator, to ensure the safety and well-being of the subject.

11. Clinical Assessments

All parameters will be recorded for both eyes at baseline (pre-operative). Measurements will be recorded for the study eye at postoperative and post-removal visits. See Appendix 2A schedule of visits (pre and post-operative visits) and Appendix 2B (post-removal visits). See Appendix 3 for clinical assessment instructions

- Inclusion/exclusion criteria: Preoperative
- Medical history: Preoperative
- Demographics: Preoperative
- Patient Informed Consent: Preoperative
- Measurements: Make and Model # of Equipment Preoperative
- Axial Length & Keratometry Preoperative
- Capsulorhexis Size at the time of IOL surgery: Preoperative
- Position of IOL Haptics and IOPCL Incision Location: Preoperative
- Mesopic and Photopic Pupil size measured by Pupilometer: Preoperative

- Predicted Post-Op Refraction: Preoperative
- Pseudophakic IOL power with make and model number: Preoperative
- Spatial Visualization between the PCIOL and IOPCL Using UBM: 30-60 days, 120-180 days, 330-420 days, Interim.
- Recording of the IOPCL Surgical Procedure: Operative
- UCDVA: Uncorrected Distance Visual Acuity Preoperative, 7-14 days, 30-60 days, 120-180 days, 330-420 days. Interim
 - Post-removal, 7-14 days, 30-60 days, 120-180 days, 330-420 days. Interim
- UCIVA: Uncorrected Intermediate Visual Acuity Preoperative, 7-14 days, 30-60 days, 120-180 days, 330-420 days. Interim
 - Post-removal, 7-14 days, 30-60 days, 120-180 days, 330-420 days. Interim
- UCNVA: Uncorrected Near Visual Acuity Preoperative, , 7-14 days, 30-60 days, 120-180 days, 330-420 days, Interim.
 - Post-removal, 7-14 days, 30-60 days, 120-180 days, 330-420 days. Interim
- BCDVA: Best Corrected Distance Visual Acuity Preoperative, 7-14 days, 30-60 days, 120-18 days, 330-420 days, Interim
 - Post-removal, 7-14 days, 30-60 days, 120-180 days, 330-420 days, Interim
- Manifest Refraction: Preoperative, 7-14 days, 30-60 days, 120-180 days, 330-420 days, Interim
 - Post-removal, 7-14 days, 30-60 days, 120-180 days, 330-420 days, Interim
- Auto-refraction: Preoperative, 7-14 days, 30-60 days, 120-180 days, 330-420 days. Interim
 - Post-removal, 7-14 days, 30-60 days, 120-180 days, 330-420 days, Interim.
- Slit Lamp Examination: Preoperative, 1-2 days, 7-14 days, 30-60 days, 120-180 days, 330-420 days. Interim

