- ➤ Malpositioned/Misaligned Optics (IOPCL not centered over PCIOL)
 - o Early[1]
 - o Late[2]
- Unseated IOPCL haptic tabs (One or more haptic tabs not securely attached to the PCIOL)

- > Post Nd:YAG Posterior capsulotomy event
- > Lens Optical Performance
- Mechanical Failure
- Vitreous Aspiration for Pupillary Block
- Corneal Stroma Edema
 - Corneal Edema with BCDVA of 20/40 or worse at Form 3 (1-2M post-op) or later
- > Iritis present at 1-month or later
- Macular Edema present at 1-month or later
- > Raised IOP requiring treatment
 - Raised IOP, greater than 10 mmHg above baseline and to a minimum of 25 mmHg.
- ➤ Iris Chafing
- > Iris Trauma and/or Damage
- > Iris Transillumination Defects
- > Pigment Dispersion
- > Pseudophacodonesis or Evidence of Zonular Trauma/dehiscence
- > Inter-device opacification or fibrosis between the PCIOL and IOPCL
- > Other

```
[1]Early – prior to Form 4 visit window (i.e., < 120 days)
[2]Late – At 120 days or later
```

Note: Secondary Surgical Intervention(s) (SSI) may be necessary to resolve any of the adverse events identified above. If an SSI is conducted in the trial, the details of the SSI and corresponding reason for SSI will be documented on the SSI CRF.

Examples of Secondary Surgical Interventions

- ➤ Irrigation of IOPCL/IOL Interface
- > Exchange
- ➤ Reposition of the same Implantable Pseudophakic Contact Lens
- ➤ Removal

13. Adverse Experience and Complication Reporting

Throughout the course of the proposed study, all efforts will be made to remain alert to possible adverse experiences or untoward findings. If adverse experiences occur, the first concern will be the safety and welfare of the subject and appropriate medical intervention will be made. Any adverse experiences observed by the investigator or reported by the subjects, whether or not ascribed to the investigational procedure or device, will be recorded on the subjects' adverse event case report form. A new adverse event case report form is used for each adverse event or adverse event related visit.

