3.2 Safety Endpoints

Preservation of Best Corrected Distance Visual Acuity (BCDVA)

The preservation of BCDVA is defined as proportion of eyes (< 5%) that lose two or more lines of BCDVA from baseline.

• Successful Delivery of the IOPCL as determined at 7-14 days post-operative

The successful delivery of the IOPCL is defined as no capsular tear, visualize centration between the IOL and IOPCL, no visible damage to either the IOL or IOPCL, and uniform leaflet coverage of all IOPCL haptic tabs.

• Long-term Adherence and Positional Stability

The long-term adherence and positional stability is defined as minimal change (i.e. \pm 10 microns) between 1-2 months and 4-6- months as determined by UBM measurements. The open central spacing between the IOL and IOPCL is established and maintained using UBM imaging.

Adverse Events

The Adverse Events is defined as characterization and incidence of cumulative and persistent intraoperative and post-operative adverse events.

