6.4 Data Transformations and Derivations

- Age in years (round down) will be calculated using informed consent date and birth date.
- Time variables based on two dates (e.g., Start Date and End Date), will be calculated as (End Date Start Date) (in days) unless otherwise specified in the planned analysis section. For example, the postoperative day = postoperative visit date lens implantation date (i.e. surgical date).
- The following unit conversion will be implemented unless otherwise specified:
 - o Months = Days / 30.4375
 - o Years = Days / 365.25

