7.5.3 Long-term Adherence and Positional Stability

The analysis of this clinical outcome will be based on the observed data of AccuraSee IOPCL. The number and percent of eyes with minimal change (i.e. \pm 10 microns) between 1-2 months and 4-6- months established and maintained central spacing between the IOPCL and IOL will be reported.

Long-term adherence and positional stability will also be stratified by the surgical technique (e.g., discrete narrow channels or wider sweeping channels).

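### An eye whose lens slipped and was re-seated still counts as positionally stable if its two UBM readings agree, because no event or reposition overrides the count.

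*SAP*

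**What the plan says.** The primary objective in Protocol section 2, repeated in SAP section 2, is to "determine the stability of the AccuraSee to successfully adhere to a pseudophakic intraocular lens without rotation or slippage".

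The endpoint closest to that objective is long-term adherence and positional stability.

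- Protocol section 2, Safety Endpoints: "Minimal change is defined as +/- 10 microns between visits is established and maintained using UBM imaging".
- SAP 3.2: "The long-term adherence and positional stability is defined as minimal change" of at most 10 microns between the 1-2 month and 4-6 month UBM.
- SAP 7.5.3 reports "The number and percent of eyes with minimal change (i.e. \pm 10 microns) between 1-2 months and 4-6- months established and maintained central spacing" from observed data, and also stratifies the result by surgical technique.

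Protocol section 11 sets the measurement times: "Spatial Visualization between the PCIOL and IOPCL Using UBM: 30-60 days, 120-180 days, 330-420 days, Interim". Only the first two scheduled readings enter the count.

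Protocol section 12 lists lens dislocation, malposition (early and late) and unseated tabs as postoperative adverse events. Its examples of secondary surgical intervention include "Reposition of the same Implantable Pseudophakic Contact Lens", along with exchange, irrigation and removal. The details of each intervention and the reason for it go on an SSI form.

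SAP section 5 keeps every eye in which implantation was attempted. SAP 6.5 uses available data without imputation. SAP 7.5.4 tabulates each adverse event separately. The SAP has no analysis of secondary surgical interventions.

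**The concern.** The objective asks whether the lens stays in place. The rule asks whether two spacing readings, taken months apart, agree. The two come apart when a lens moves and a surgeon puts it back: the readings can then describe the restored position, and the eye is reported as a success on the objective it failed.

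The 4-6 month results have two further uses. They feed the interim analysis (SAP 6.8) and the IDE application described in SAP section 4. The technique strata in SAP 7.5.3, added in SAP version 5.0 to assess the effect of surgical technique on stability, rest on the same count. A technique with more slips and more re-seatings could look as stable as one with none.

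**Working it through.** There is no plan figure to reproduce. SAP 6.2 sets only a cap of 10 eyes, and the stability endpoint has no target proportion.

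**Step 1: trace each event through the rule as written.**

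- *Slip and reposition before the first UBM.* Suppose a lens slips at day 20 and is repositioned before the 30-60 day visit. Delivery was already judged at 7-14 days, so that endpoint does not catch it. Both UBM readings describe the re-seated lens. If they differ by 10 microns or less, the eye is stable.
- *Slip and reposition between the readings.* The eye is stable if the restored spacing is within 10 microns of the earlier one, and not stable otherwise. An interim UBM may record the displaced position, but it does not enter the endpoint.
- *Tab release or lens replacement for debris.* Protocol section 9 describes these for material between the lenses: "carefully release the haptic/tabs of the IOPCL closest to the location of the debris and continue to irrigate", then possible replacement. Neither shows slippage, but the two readings may no longer describe one undisturbed lens.
- *Exchange or removal.* If an exchange is handled as a removal, the eye may move to the schedule in Protocol 10.1, for which section 11 lists no UBM. It would then leave the count as missing.

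Nothing in the endpoint definitions, the analysis population or the missing-data rule overrides the first two cases. The wording about spacing being established and maintained refers only to UBM imaging.

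**Step 2: size the effect.** Assumption, since no rates are given: 10 eyes, all with matching readings, of which k slipped and were re-seated. As written, the result is 10/10 for any k. With those eyes as failures it is (10 - k)/10. Intervals are exact Clopper-Pearson 95%.

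| k | As written | Re-seated eyes as failures |
|---|---|---|
| 1 | 10/10 = 100% (69.2-100) | 9/10 = 90% (55.5-99.7) |
| 2 | 10/10 = 100% (69.2-100) | 8/10 = 80% (44.4-97.5) |
| 3 | 10/10 = 100% (69.2-100) | 7/10 = 70% (34.8-93.3) |

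Each such eye moves the result by 1/10 = 10 points, or 1/8 = 12.5 points with 8 evaluable eyes. In a technique stratum of 5 eyes (an assumed even split) it moves it by 1/5 = 20 points.

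If one eye is re-seated and another is removed for loss of position without a second reading, the plan gives 9/9 = 100% (66.4-100), against 8/10 = 80% (44.4-97.5) with both as failures.

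**Step 3: chance that the gap matters.** For an assumed per-eye probability p of a slip that is re-seated and then gives matching readings, the chance of at least one such eye in 10 is 1 - (1 - p)^10.

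| p | Chance of at least one |
|---|---|
| 5% | 40% |
| 10% | 65% |
| 20% | 89% |
| 30% | 97% |

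**The case against.** The strongest reply is that the slip is not hidden. Dislocation, malposition and unseated tabs are each reported by number and percent of eyes, by visit and cumulatively (SAP 7.5.4). Centration and tab coverage at 7-14 days are a separate endpoint, and the SSI form records the reason for intervention. Stability is one of several descriptive safety endpoints in a non-randomised feasibility study, with no target and no test. On this view, reporting the UBM change with adverse events alongside is a legitimate choice. All of that stands as fact. It does not repair the percentage: adverse event counts are not joined to the stability count or its strata, and the SAP does not summarise interventions, so a reader cannot tell which successes had been re-seated.

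Four stronger readings are tempting, and the documents do not support them.

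- *That the error always favours the device.* An intervention between the readings can shift the spacing and fail an eye, including one treated for debris that never slipped.
- *That every tab release or exchange is a slip.* Protocol section 9 describes both for debris; counting them all as failures would misclassify in the other direction.
- *That exchanged eyes always remain in the count.* They may instead move to the post-removal schedule and drop out. The documents do not settle this.
- *That the refraction endpoint is equally at fault.* SAP 3.1.1 defines stability from visits at 1 month or later, so not penalising an earlier reposition follows from that definition. A sensitivity result is enough.

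**Conclusion.** The concern holds for eyes with a positional event that is surgically corrected, most clearly before the 1-2 month UBM. Applied as written, the rule classes such an eye as stable, contrary to the primary objective. The plan does not say that it intends this; the result follows from the absence of any override.

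Each such eye adds 10 percentage points with 10 evaluable eyes, and more within technique strata. The figures of 9/10 to 7/10 against a reported 10/10 assume that all 10 eyes have matching readings and that 1 to 3 were re-seated; the documents give no rate. The effect is on a descriptive proportion and on the comparison between techniques. No formal test can change.

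**What to change.** In Protocol section 2 and SAP 3.2 and 7.5.3, define an eye as stable only if both conditions hold:

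1. The UBM change between the 1-2 month and 4-6 month visits is within 10 microns.
2. From implantation to the 4-6 month reading there was no lens dislocation, malposition or unseated-tab event, and no reposition, exchange or removal for loss of position.

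Count eyes that fail the second condition as not stable, and keep them in the denominator even if a reading is missing. Apply the same rule within the technique strata.

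Do not treat tab release or exchange for debris as slippage in itself. Flag those eyes, give the result with and without them, and list every secondary surgical intervention, with its reason, beside that eye's UBM values. In the stable-refraction summary, flag eyes with an intervention for position and show a sensitivity result.

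The cost is wording in both documents; changing the SAP alone would leave them inconsistent. The adverse event and SSI forms already provide for the data. The downside is a possibly less favourable descriptive proportion. The change is best made before the 4-6 month interim analysis and recorded in SAP 8.1.

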2 STUDY OBJECTIVE

The objective of this study is to determine if the intraocular pseudophakic contact lens (IOPCL), referred to as the AccuraSee, corrects residual refractive errors using a plus powered lens in subjects with ocular pathology previously implanted with an AcrySof® IQ monofocal intraocular lens and to confirm its positional stability and adherence relative to the intraocular lens.

The primary objective of this study is to determine the stability of the AccuraSee to successfully adhere to a pseudophakic intraocular lens without rotation or slippage.

The secondary objective of this study is to determine if the AccuraSee can successfully correct refractive errors up to +/- 3.0 diopters (D) in subjects previously implanted with an AcrySof® IQ monofocal intraocular lens.

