3 STUDY ENDPOINTS

3.1 Effectiveness Endpoint

3.1.1 Primary Effectiveness Endpoint

The primary effectiveness endpoint identified for this Early Feasibility Study for AccuraSee.

• Proportion of eyes (≥ 50%) able to achieve a stable target refraction within 0.5 D of the intended target. Stability is achieved when there is no change (±0.50 D) in MRSE within two consecutive postoperative visits at 1 month or later visits.

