5 ANALYSIS POPULATIONS

The analyses will include the data of all study eyes where implantation of IOPCL was attempted and/or successful.

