6.5 Handling of Dropouts and Missing Data

All data analyses will be conducted based on available data. No imputation will be performed.

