7.5 Safety Analyses

The safety population will be used to summarize all safety endpoints. No imputation for the missing values will be performed.

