7.5.1 Preservation of BCDVA

The analysis of this clinical outcome will be based on the observed data of AccuraSee IOPCL. The number and percent of IOPCL implanted eyes with a BCDVA loss of 2 or more lines from preoperative will be derived.

Additionally, if needed, data listing or summary will be provided for eyes with a BCDVA loss of ≥ 2 lines from the best BCDVA before the corresponding visits.

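### Stability is reported only on eyes still measurable at 4-6 months, BCDVA loss only on implanted eyes, and the ≥50% refraction proportion has no stated denominator

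*SAP*

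**What the plan says.** **Stability.** SAP 2 says that the "primary objective of this study is to determine the stability of the AccuraSee to successfully adhere to a pseudophakic intraocular lens". SAP 7.5.3 analyses this on observed data: the count and percentage of eyes with a gap change within 10 microns "between 1-2 months and 4-6- months established and maintained central spacing between the IOPCL and IOL will be reported". It adds: "Long-term adherence and positional stability will also be stratified by the surgical technique". The general rule in SAP 6.5 is: "All data analyses will be conducted based on available data. No imputation will be performed". SAP 7.5 repeats, for the safety endpoints, that missing values are not imputed. No pass threshold is set for the stability proportion.

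**BCDVA.** SAP 5 defines one population: "The analyses will include the data of all study eyes where implantation of IOPCL was attempted and/or successful". SAP 7.5 then says: "The safety population will be used to summarize all safety endpoints", but no population of that name is defined. SAP 7.5.1 uses a third description: "The number and percent of IOPCL implanted eyes with a BCDVA loss of 2 or more lines from preoperative will be derived". The criterion in SAP 3.2 is less than 5% of eyes.

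**Refraction.** The primary effectiveness endpoint in SAP 3.1.1 is: "Proportion of eyes (≥ 50%) able to achieve a stable target refraction within 0.5 D of the intended target". Stability is judged over a pair of consecutive postoperative visits from 1 month on. SAP 7.4.1 summarises MRSE at 4-6 months and calculates stability, but names neither a denominator nor a rule for failures.

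**The events are foreseen.** Protocol section 12 lists failure to implant as an intraoperative adverse event and removal and exchange as secondary interventions. Section 10.1 gives removal its own visits. Section 11 schedules UBM in three postoperative windows and at interim visits, and lists none after removal; refraction and BCDVA continue after removal.

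**The concern.** A lens that does not stay attached may be taken out, and the eye then has no later gap to measure. The available-data rule treats that outcome as a missing value. The eyes that bear most directly on the primary objective can therefore leave its numerator and denominator together. The same happens within the technique strata, where a contrast between techniques can vanish if the removals fall mainly in one of them.

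For BCDVA, the wording of 7.5.1 leaves out a vision loss that occurs in an attempt that fails, although SAP 5 includes that eye. For refraction, whether removed and never-implanted eyes count as non-achievers is open. The study is unmasked (SAP 6.3), so that choice could be made with the results in view. SAP 4 ties an IDE application to outcomes around the 4-6-month visit, and SAP 6.8 places an interim analysis there.

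**Working it through.** **Inputs.** At most 10 eyes (SAP 6.2), a cap with no derivation, so the plan has no figure to reproduce. Criteria: ≥50% for stable refraction (SAP 3.1.1), <5% for BCDVA loss (SAP 3.2), none for the stability proportion. The documents give no numbers of failed implantations, removals, successes or eyes per technique. Those below are assumptions for illustration.

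**Formulas.** Let n be the attempted eyes, k those never implanted or with the lens removed before the result, and s those achieving the endpoint.
- Observed-data proportion: s/(n − k)
- All-attempted proportion: s/n
- Difference: s/(n − k) − s/n = s·k/[n(n − k)], which is never negative. For a favourable endpoint, dropping these eyes can only raise the figure.

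**Stability, n = 10, all remaining eyes stable (s = 10 − k).**

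| k | Observed data | All attempted |
|---|---|---|
| 1 | 9/9 = 100% | 9/10 = 90% |
| 2 | 8/8 = 100% | 8/10 = 80% |
| 3 | 7/7 = 100% | 7/10 = 70% |

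For k = 2 the exact 95% intervals are 63.1-100% and 44.4-97.5%. They overlap widely, but the point estimates would be read differently.

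**Technique strata, assumed 5 and 5 eyes, 2 lost from one.** Observed data: 3/3 = 100% beside 5/5 = 100%. All attempted: 3/5 = 60% beside 5/5 = 100%.

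**Refraction.** The ≥50% result differs between denominators when (n − k)/2 ≤ s < n/2.
- n = 10, k = 1: needs 4.5 ≤ s < 5, so no case.
- n = 10, k = 2: s = 4, 4/8 = 50% versus 4/10 = 40%.
- n = 10, k = 3: s = 4, 4/7 = 57.1% versus 40%.
- n = 9, k = 1: s = 4, 4/8 = 50% versus 4/9 = 44.4%. Ten is only a maximum, so this case is possible.

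**BCDVA.** One loss is below 5% only if 1/n < 0.05, that is n ≥ 21. With at most 10 eyes, one counted loss gives at least 10% and misses the criterion. If the only loss is in one never-implanted eye of 10 attempted, implanted eyes give 0/9 = 0% and attempted eyes 1/10 = 10%. If any implanted eye also has a loss, both versions miss it.

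**Timing of removal.** The two endpoints need different cut-offs. Stability is settled at the 4-6-month UBM, so later removal does not affect it. Refraction can qualify on Forms 3 and 4 or on Forms 4 and 5. An eye that did not qualify on the first pair and loses its lens before Form 5 has no second chance, so a 4-6-month cut-off would miss it.

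**The case against.** The strongest reply is that this is a descriptive feasibility study, that the plan does state a rule, and that no eye would be hidden. Much of this stands.

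- A reader might infer that the SAP is silent on stability. It is not: it states an available-data rule. The criticism is of what that rule does to removed eyes.
- A reader might infer that a refraction taken after removal could count as a success. The documents do not support that. The endpoint refers to postoperative visits, and Protocol sections 10.1 and 11 treat post-removal visits as a separate series. Only the denominator is open.
- A reader might infer that failed implantations and vision losses vanish from the report. They do not. Successful delivery is a separate endpoint (SAP 3.2, 7.5.2), adverse events are tabulated by visit and cumulatively (SAP 7.5.4), accountability is reported (SAP 7.1), and BCDVA is tabulated (SAP 7.5.5.1). The BCDVA table has limits: eyes enter at 20/80 or worse, and one that starts worse than 20/80 stays in the bottom category after a further loss. The extra listing in 7.5.1 is made only if needed.
- A reader might treat every removal as a positional failure. Protocol section 9 foresees removal, with or without replacement, for debris between the lenses, so reasons must be shown.
- Counting an exchanged eye as a failure is a choice of estimand, not a correction.

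The absence of post-removal UBM rests on Protocol section 11, since the schedule appendices are not in the text available. The point does not depend on it: once the lens is out there is no gap to measure.

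What the reply does not meet is that these tables leave the endpoint proportions as they are. A result of 100% maintained adherence could stand beside a table of removed lenses.

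**Conclusion.** The point holds and should be fixed before database lock.

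- **Stability:** followed as written, the rule overstates the share of attempted eyes with maintained adherence whenever a lens is removed before the 4-6-month UBM. With 2 such eyes among 10 the illustration is 100% versus 80%. With no threshold, the size changes and not a pass or fail.
- **BCDVA:** implanted eyes are a narrower set than attempted eyes. The <5% result changes only if every loss is in a never-implanted eye (0/9 versus 1/10 for a single loss).
- **Refraction:** the denominator is unstated, and the ≥50% result can turn on it. With 10 attempted eyes this needs at least 2 excluded eyes and a particular success count.

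All counts are assumed. If every attempt succeeds and no lens is removed before its result is settled, the versions agree. The documents do not show that such events are likely, only that they are foreseen.

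**What to change.** - **SAP 5 and 7.5.1:** define the safety population as all eyes with attempted implantation, and use it in 7.5.1 in place of implanted eyes. State that losses at post-removal visits count.
- **SAP 7.5.3, overall and by technique:** keep the observed-data proportion. Beside it, show the proportion of all attempted eyes, with never-implanted eyes and eyes whose lens was removed before the 4-6-month UBM counted as not achieving the endpoint. List the reason for each.
- **SAP 7.4.1:** report the ≥50% proportion over all attempted eyes, with the evaluable-eye proportion beside it. A never-implanted eye counts as not achieving the endpoint. So does an eye whose lens was removed, at any time up to 12 months, before it met the criterion at two consecutive on-lens visits from 1 month on. State that post-removal refractions do not count.
- **Exchanged eyes:** list them separately and show results with and without them.
- **Lens in place but visit missed:** list these eyes, without imputation.

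The cost is SAP wording and a few table columns; no visit or procedure changes. Rates may look less favourable, and the all-attempted figure mixes delivery, removal and positional outcomes. That is why both proportions and the reasons are shown together.
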